## 4.3.2 Definitions for adverse events and reactions

The following definitions will be used:

Adverse event (AE): any untoward medical occurrence in a subject to whom a medicinal product is administered and which does not necessarily have a causal relationship with this treatment.

Adverse reaction (AR): all untoward and unintended responses to an investigational medicinal product related to any dose administered.

Serious adverse event (SAE): any untoward medical occurrence that at any dose requires inpatient hospitalization or prolongation of existing hospitalization, results in persistent or significant disability or incapacity, results in a congenital anomaly or birth defect, is life-threatening, or results in death.

Serious adverse Reaction (SAR): an adverse drug reaction that is serious (see above) and at least possibly related to an investigational medicinal product related to any dose administered.

Suspected unexpected serious adverse reaction (SUSAR): a serious adverse reaction, the nature, severity or outcome of which is not consistent with the reference safety information.

## 4.3.3 Reporting

Serious adverse reactions and events (SAE and SARs) and suspected unexpected adverse reactions (SUSARs) will be recorded daily in the eCRF during the intervention period. PI is to report potential SARs and SUSARs without undue delay to the sponsor, which in turn will evaluate the event according to the Danish summaries of product characteristics and report any SAR's and/or SUSARs, which in turn will report these to the Danish Health and Medicine Authorities 7 days at the latest after the report has been received. The sponsor will yearly submit a list of all registered AEs that have occurred during the trial period as well as a report on safety (SAR) of the trial subjects to the Danish Medicines Agency and Scientific Ethics Committee.

The sponsor will notify the Danish Medicines Agency when the trial has been completed (no later than 90 days thereafter). The results from the clinical trial including important adverse events will be recorded on EudraCT.

#### 5. SAMPLE SIZE CALCULATION AND STATISTICAL ANALYSIS PLAN

## 5.1 Sample size calculation

We consider a mean reduction in pain intensity of 1 (SD  $\pm$ 2) on the NRS scale to be realistic in the control group and that the reduction should be 2.5 (SD  $\pm$  2) in the intervention group for the addition of LDK to be meaningful. Based on these estimates, an alpha of 5%, a power of 90% and a two-sample t-test (assuming that the pain reduction is normally distributed), a sample size of 78 patients is required; 39 in each treatment arm (two independent samples =156 patients).

The primary (continuous) and secondary outcomes (binary and continuous variables) will be presented as follows: Categorical variables will be compared using Fisher's exact test and continuous variables

using t-tests or Wilcoxon rank-sum test as appropriate. P < 0.05 will be considered statistically significant.

To investigate the hypothesis of heterogeneity in effect of LDK addition depending on prior morphine use, we will compare treatment effect between the two groups (no prior morphine use vs prior morphine use). If we assume the two groups to have equal size (78 patients) then the expected SE of the difference between treatment effects of the two groups (no prior morphine vs prior) will be 0.64, i.e. the corresponding 95% confidence interval will have a width of approximately 2.6.

To handle potential differences in baseline pain intensity between the standard and the LDK treatment group, we will assess the relative (%) change in NRS from baseline (T0) to 10 min after administration of study medicine in a supplemental post-hoc analysis. The relative change in pain scores will be assessed by multilevel mixed effect ordinal logistic regression model.

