#### 2.2 ALLOCATION

Patients fulfilling all inclusion criteria and no exclusion criteria will be randomized as follows:

Group 1 = patients with a prior use of opioids.

Group 2 = patients without a prior use of opioids.

Patients in group 1 are allocated randomization numbers 101-190

Patients in group 2 are allocated randomization numbers 201-290

There are 10 additional numbers in each group to be used if a patient is excluded after the administration of study medicine.

If a patient is excluded after randomization, but before study medicine is administered, the randomization number can be re-used by adding and registering a, b, c and so on.

Patients (n=160) will be randomized in a 1:1 ratio to either s-ketamine or placebo (NaCl) in blocks of 2, 4 and 6 patients

The randomization process will be performed by the hospital pharmacy using www.sealedenvelope.com.

The randomization list is kept at the hospital pharmacy during the study and only delivered to the PI when the inclusion and the data analysis are completed.

PI will be provided with numbered blinded kits including either S-ketamine or placebo ensuring allocation concealment.

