#### 4.1.2 Rationale

This study is powered to detect a difference in pain reduction of at least 1.5 on the NRS scale between the groups. (LDK vs placebo)

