#### 5.2 General considerations

The statistical analyses and reporting will adhere to the CONSORT guidelines.. All tests will be two-sided, a p-value < 0.05 will be considered significant, and all confidence intervals will have 95% coverage.

Patient inclusion and exclusion will be illustrated in a CONSORT flow diagram (see Appendix 3).

We will include measures related to feasibility including the enrolled to screened ratio, time to randomization, and protocol adherence/major protocol violations. All analyses will be conducted in the modified intention-to-treat (MITT) population defined as all randomized participants for whom consent was obtained.

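### The supplemental analysis meant to handle unequal baseline pain names a multilevel ordinal model for what reads as one value per patient, and neither document names a baseline-adjusted comparison of the arms

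*Combined protocol and SAP*

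**What the plan says.** Protocol section 5.1 first plans unadjusted comparisons (t-test or Wilcoxon rank-sum for continuous outcomes). It then gives its answer to unequal starting pain between the standard and ketamine arms. The response is the "relative (%) change in NRS from baseline (T0) to 10 min after administration of study medicine in a supplemental post-hoc analysis", and the model is given in the next sentence: "The relative change in pain scores will be assessed by multilevel mixed effect ordinal logistic regression model". The section names no clustering level, random effect, category boundaries or baseline covariate.

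Sections 2.1.3 and 3.1 describe one hospital, with a possible second emergency department only by amendment. Section 2.5.1 schedules NRS at T0 and at 10, 20, 30, 45, 60 and 120 minutes. Section 2.2 randomises from separate number ranges for patients with and without prior opioid use.

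The SAP of September 2023 does not mention the ordinal model. It has a multilevel linear regression for NRS over the time points, conditional on normality and with no baseline term named. Its one provision for T0 differences is an unspecified test tied to the two prior-opioid groups, not to the treatment arms.

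**The concern.** Two things do not fit together.

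- **Model and response.** A multilevel model needs several rows per cluster. A percent change from T0 to 10 minutes gives one row per patient. A patient random intercept then competes with the logistic residual to explain the same scatter, and the patient-specific odds ratio scales with whatever variance the software settles on.
- **Response and purpose.** Dividing by T0 is not the same as adjusting for T0. It removes the effect of an imbalance only if the 10-minute score is proportional to T0.

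At stake is whether the protocol's one stated provision for unequal T0 pain between arms can be programmed as written and does what it is for.

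**Working it through.** **1. The plan's own figure.** Section 5.1 uses "an alpha of 5%, a power of 90% and a two-sample t-test", reductions of 1 and 2.5 and an SD of 2 in each arm; section 4.1.2 says the trial is powered to "detect a difference in pain reduction of at least 1.5 on the NRS scale between the groups".

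Normal approximation: n per arm = 2(1.960 + 1.282)² × 2²/1.5² = 2 × 10.51 × 1.778 = 37.4, so 38. The exact two-sample t-test gives 38.35, so 39 per arm with 90.5% power. This matches "a sample size of 78 patients is required; 39 in each treatment arm". The interaction standard error, √(4 × 4/39) = 0.64, also matches. Neither figure uses the ordinal model.

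**2. Random intercept with one row per patient.** Write the latent response as β·arm + u + e, with u having SD σ and e logistic. The data mainly fix β/√(1 + 0.346σ²), where 0.346 = (16√3/15π)² is the usual logistic-normal constant. So, approximately,

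log OR(σ) ≈ log OR(0) × √(1 + 0.346σ²).

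For OR(0) = 3.64 (log 1.292), σ = 3 gives exp(1.292 × 2.028) = 13.7, and σ = 5 gives exp(1.292 × 3.106) = 55.

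Simulation inputs from the documents: reductions 1 and 2.5, SD 2, n = 116 (SAP) or 156 (protocol). Assumptions: T0 mean 7.3 and SD 1.4, scores rounded, T0 kept within 5–10 and the 10-minute score within 0–10, equal arms, percent change cut at 0, 20, 40 and 60 into five categories. The models were fitted by Gauss-Hermite quadrature with σ held fixed. Two of six trials:

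| σ | n=116: −logL | OR | n=156: −logL | OR |
|---|---|---|---|---|
| 0 | 172.10 | 3.64 | 237.68 | 2.78 |
| 1 | 172.20 | 4.56 | 237.64 | 3.37 |
| 2 | 172.31 | 7.50 | 237.60 | 5.12 |
| 3 | 172.35 | 13.89 | 237.59 | 8.53 |
| 5 | 172.39 | 54.4 | 237.61 | 25.75 |

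Over all six trials, the odds ratio was 2.5 to 4.5 at σ = 0 and 14 to 113 at σ = 5. The log-likelihood never moved by more than 0.67. In a separate set of 40 trials (n = 116), the median odds ratio was 3.6 at σ = 0 and 14.6 at σ = 3, with a largest log-likelihood difference of 1.3. A 95% likelihood interval needs a drop of 3.84/2 = 1.92, so no trial in that set could tell σ = 0 from σ = 3.

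**3. Does percent change remove baseline?** Suppose there is no treatment effect and the mean 10-minute score is 6.3 + s(T0 − 7.3), that is, a reduction of 1 at the assumed mean T0. Then

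mean percent change = 100 × [1 − s − (6.3 − 7.3s)/T0].

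This is free of T0 only when s = 6.3/7.3 = 0.86. For arm means of 7.3 and 7.8, the spurious arm difference is about 100(6.3 − 7.3s)(1/7.3 − 1/7.8) = 0.878(6.3 − 7.3s) percentage points. The simulation used n = 156 and 2,000 trials per slope, with the 0.5-point imbalance imposed before rounding and limiting.

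| Slope s | Formula, % points | Simulated, % points | Change score, NRS points | With T0 covariate, NRS points |
|---|---|---|---|---|
| 0.3 | 3.6 | 3.6 | 0.33 | 0.00 |
| 0.5 | 2.3 | 2.5 | 0.25 | 0.01 |
| 0.7 | 1.0 | 1.2 | 0.16 | 0.00 |
| 0.86 | 0.0 | 0.3 | 0.09 | 0.00 |
| 1.0 | −0.9 | −0.3 | 0.05 | 0.02 |

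The simulated and formula values differ mainly because scores are rounded and bounded. For scale, the planned 1.5-point effect is 1.5/7.3 = 20.5 percentage points at the assumed mean. The imbalance tested is large for chance: its standard error with 78 per arm is 1.4 × √(2/78) = 0.22, so 0.5 is about 2.2 standard errors.

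**The case against.** The strongest reply is that the level is inferred. Section 5.1 states no row structure, its second sentence speaks of pain scores without a time point, and NRS is taken seven times. With all scores as rows, a patient intercept would have repeated data. This stands as far as it goes: the certain defect is an unspecified level, rows and categories. But the only response the section defines is the single T0-to-10-minute percent change, and on that reading the mismatch follows.

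A reader might infer that no odds ratio can be estimated, or that the fit would fail to converge. Neither is supported. Strictly, the ordinal model is weakly identified through the shape of the link. Without the random intercept the proportional-odds ratio is estimable, and non-convergence was not shown. The test of arm also barely depends on σ. In 40 simulated trials the median likelihood-ratio chi-square was 13.3 at σ = 0 and 13.9 at σ = 3 and at σ = 5, and the p < 0.05 conclusion agreed in 39. Only the size of the conditional odds ratio is arbitrary.

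A reader might also infer that baseline is not handled at all. Percent change is a partial adjustment. If each patient's reduction does not depend on T0 (slope 1.0), it left only −0.3 points, and the worst case of 3.6 rests on an assumed slope of 0.3. It is also true that the primary outcome is already a change from T0. But a change score leaves its own residue (0.33 to 0.05 NRS points above), and the documents give no slope on which to rely.

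Finally, the analysis is supplemental, the SAP dropped it, and the SAP refers to a detailed plan in the Trial Master File that is not public. That limits the consequence. It does not supply a baseline-adjusted arm comparison in either document.

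**Conclusion.** The point holds as a specification defect in a supplemental analysis. Read literally, the model does not match a response with one value per patient. If the random effect is a patient intercept, the conditional odds ratio depends on a variance that the data cannot determine: in the simulations it rose from about 3–4 to tens, or above 100, with almost no change in fit. Percent change removes a T0 imbalance only near one slope of the 10-minute score on T0. Away from that slope the residue was up to 3.6 percentage points, against a planned effect of about 20, for a fairly extreme imbalance. A T0 covariate left at most 0.02 NRS points at every slope tried.

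These sizes rest on the assumed T0 distribution, category cuts, slopes and patient-level random effect. The direction of both findings follows from the algebra.

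It would be tempting to conclude that the trial's main result is at risk. The documents do not support that: the primary comparison and the sample size do not use this model. What is missing is a workable baseline-adjusted comparison of the arms, which the protocol wanted and the SAP does not name.

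**What to change.** Replace the two sentences in protocol 5.1, and add a matching sentence to the SAP, which has none to replace. For example: the 10-minute NRS will be compared between arms in a single-level model (linear ANCOVA, or proportional odds on the 0–10 score; state which) with arm, T0 NRS and prior-opioid group as covariates, reporting the arm effect with its 95% confidence interval.

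If a multilevel model is wanted, fit it to all post-dose NRS scores from 10 to 120 minutes with a patient random effect and T0 NRS as covariate, and report the arm contrast at 10 minutes.

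The cost is a few sentences. T0 NRS and all later scores are already scheduled, and randomisation already runs within the prior-opioid groups, so no new data are needed and the sample size stands. The change should be dated before the allocation is opened, or else reported as added afterwards.

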#### 5.2 General considerations

The statistical analyses and reporting will adhere to the CONSORT guidelines.. All tests will be two-sided, a p-value < 0.05 will be considered significant, and all confidence intervals will have 95% coverage.

Patient inclusion and exclusion will be illustrated in a CONSORT flow diagram (see Appendix 3).

We will include measures related to feasibility including the enrolled to screened ratio, time to randomization, and protocol adherence/major protocol violations. All analyses will be conducted in the modified intention-to-treat (MITT) population defined as all randomized participants for whom consent was obtained.

#### 6. DATA COLLECTION AND DATAMANAGEMENT

## 6.1 Data collection process

The site investigator (PI) is responsible for data collection and entry. This will include the patient identifier (i.e. Danish Central Personal Register number), study ID, and timing of enrollment. Data will be obtained in eCRFs especially regarding pain therapy as well as from medical journals; all data will be based on measurements and assessments made by the clinical team. Data are continuously entered

into RedCap (Institute for Clinical Medicine, Aarhus University), which is considered as the Case Report Form. RedCap is a secure web application geared to support data capture for research studies

6.2. Variables

6.2.1 Overview

All patients admitted to the ED during study days with a painfull condition AUH, will be entered into a screening log. For those screened but not randomized, a specific reason for non-inclusion/exclusion will be documented. All randomized patients will be entered into the main database.

A detailed data dictionary that clearly defines all included variables will be created prior to patient enrollment. The data dictionary will provide the name of the variable (including the code used in the database), a detailed definition of the variable, categories for categorical variables, and units and ranges for continuous variables.

The number of collected variables will be kept relatively small to limit resource use and data entry mistakes. Below is provided a brief overview of the included variables, but details are reserved for the data dictionary.

6.2.2 Baseline characteristics

Trial related variables

Study ID

Inclusion criteria

**Exclusion criteria** 

Opioids given before study medication (i.e. in ambulance)

Date and time consent for data collection is obtained

Patient demographics and characteristics

Unique patient identifier (CPR number)

Age

Sex

Height

Weight Medications prior to enrollment Prior opioid use, dose, duration Reason for prior opioid use (cancer/non-cancer pain, postoperative, addiction) Cancer/non-cancer Site of pain/injury: Fracture/orthopedic Abdominal/flank Groin pain Postoperative pain Other/unknown Prior to randomization: Vital parameters NRS At 10, 20, 30, 45 60 and 120 min after randomization: NRS

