## 2.5 TRIAL PROCEDURES

## 2.5.1 Patients

The trial procedures will be limited to the interventions given with the first dose of morphine (see section 2.3)

Data will be obtained from the study specific eCRF and from the electronic medical records.

 $T_0$  defined as when the ED physician/nurse evaluates NRS and the PI gives the study medication.

The trial and observation period is  $T_0$  - 120 min.

	T 0	10 min	20 min	30 min	45 min	60 min	120 min
NRS	Х	х	Х	Х	Х	Х	х

Patient rated		Х					Х
pain relief*							
Vital	Χ	Х	Х	Χ	Х	Χ	Х
parameters							
Patient		х		Х			х
reported side							
effects**							
Physician							х
reported side							
effects***							
Provider							x
satisfaction							
score****							
Patient							x
satisfaction							
score							
RASS****	 	Х	Х	Х	Х	Х	Х

\*Patients will be asked to rate their pain relief on a 6-point scale ("worse pain," "no," "little," "moderate," "good," or "complete pain relief").

In addition, patients are encouraged to spontaneously report any other side effects/adverse advent. The timing of onset and resolution of all adverse effects during the observation period will be recorded.

- \*\*\*Physician-reported side effects: nystagmus, hypertension, respiratory depression, bradycardia, hallucinations.
- \*\*\*\*Provider satisfaction with pain control will be recorded on the 4-point Likert scale with 0 being "completely unsatisfied" and 3 being "very satisfied.
- \*\*\*\*\*Richmond Agitation-Sedation Scale (RASS) will be used to evaluate agitation or sedation. (appendix 2)

TRIAGE and TOKS (tidlig opsporing af kritisk sygdom) according to the standard at AUH will be used to evaluate differences in vital parameters.

\*\*Patient-Reported Side effects: nausea, lightheadedness or dizziness, disorientation, euphoria, itching, tinnitus, double vision, abnormal dreaming or hallucinations.

There will be no questionnaires for the participants to answer, they will be asked verbally and their answers will be entered in RedCap.

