## 4.3 Safety and harm

#### 4.3.1 General consideration

The personal in the ED are highly trained in acute pain therapy. The PI is Specialty trainee in anesthesiology, Department of Anesthesiology AUH and she will be at trial site whenever study medicine is given. The doses used in this study are very low (0,1 mg/kg), and we do not expect any serious adverse reactions with this dose. We therefore believe it is safe for both individual patients and at the group level to be enrolled into this study after relevant inclusion and exclusion criteria.

The overall benefit and potential harm will be captured in our secondary outcomes, and the clinical team/PI will document any specific adverse reactions suspected to be related to the intervention - if there are AE or AR's after the observation period ( $T_0$ - $T_{120}$ ), the patients are observed as standard on AUH.

All participants are expected to receive opioids, but the amount is hypothesized to differ.

AE as natural consequences of the reason for hospitalization will not be registered in the eCRF. (i.e. blood transfusion).

Investigators should use their knowledge of the patient, the circumstances surrounding the event, and an evaluation of any potential alternative causes to determine whether or not an AE is considered to be related to the study drug, indicating "yes" or "no" accordingly. The following guidance will be taken into consideration:

- Temporal relationship of event onset to the initiation of study drug
- Course of the event, considering especially the effects of dose reduction, discontinuation of study drug, or reintroduction of study drug (where applicable)
- Known association of the event with the study drug or with similar treatments
- Known association of the event with the disease under study
- Presence of risk factors in the patient or use of concomitant medications
  known to increase the occurrence of the event
   Presence of non-treatment-related factors that are known to be associated
  with the occurrence of the event

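### With no T0 reading of side effects or RASS and no new-or-worsened rule, symptoms present before dosing can count in both arms and dilute a true ketamine excess

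*Combined protocol and SAP*

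**What the plan says.** In the protocol's section 2.5.1 schedule, only NRS and vital parameters are marked at T0. Patient-reported side effects are marked at 10, 30 and 120 min, and RASS at 10, 20, 30, 45, 60 and 120 min. Section 6.2.2 agrees: the pre-dose entry is "Prior to randomization: Vital parameters NRS", and RASS and side effects appear only in the list for 10 min onwards.

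The prompted items are given as "Patient-Reported Side effects: nausea, lightheadedness or dizziness, disorientation, euphoria, itching, tinnitus, double vision, abnormal dreaming or hallucinations". For RASS, the protocol says "Richmond Agitation-Sedation Scale (RASS) will be used to evaluate agitation or sedation".

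Three provisions bear on symptoms that precede the study drug:

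- Section 2.5.1: "The timing of onset and resolution of all adverse effects during the observation period will be recorded".
- Section 4.3.1: "AE as natural consequences of the reason for hospitalization will not be registered in the eCRF".
- Section 4.3.1 also asks investigators "to determine whether or not an AE is considered to be related to the study drug, indicating 'yes' or 'no' accordingly".

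The SAP reports the number with any adverse event during observation, and with a sedation category, compared by chi-square. It has no baseline term and does not define a new or worsened event. Protocol section 2.1.2 hypothesises that side-effect frequency will be similar in the two arms and gives no margin.

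**The concern.** Some prompted items can come from the presenting illness or from opioids as well as from study drug. Patients enter with NRS of 5 or more. Abdominal or flank pain is among the listed sites. Opioids may have been given before study medication, for instance in the ambulance. Half the planned sample uses opioids daily. Nausea, dizziness and itching can plausibly be present before dosing, and a first question at 10 min does not by itself separate them from new symptoms.

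Such symptoms fall on both arms alike. They raise both observed proportions and shrink the gap, so a real excess on ketamine becomes harder to see. That shift is towards the protocol's own hypothesis of similar frequency, and the SAP calls the trial an equivalence trial. Safety is part of the stated objective (section 2.1.5), so a weakened comparison matters even though it is a secondary outcome.

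**Working it through.** **The plan's own figure.** No rate, difference or power is stated for side effects or RASS. The only design calculation is for NRS in section 5.1: difference 2.5 - 1 = 1.5, SD 2, two-sided alpha 5%, power 90%. The two-sample t-test needs 38.35, so 39 per arm, with 90.5% power. That reproduces, and this point does not affect it.

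**Inputs from the documents.** The SAP names n = 116, about 58 per arm at 1:1. The protocol target is 160, so 80 per arm. Tests are two-sided at 5%.

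**Assumed inputs.** True new onset is 20% on placebo (qP) and 45% on ketamine (qK). The share b with the symptom at T0 runs from 20% to 50%.

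**Model.** Without T0, the observed proportion is b + (1-b)q, so the observed difference is (1-b)(qK - qP). With T0 there are two options: count new onset over all patients, (1-b)q in each arm, or analyse only patients free of the symptom at T0, with rates q and (1-b)n per arm.

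Power = Φ[(d - 1.96·SE0)/SE1], where d is the observed difference, SE0 uses the pooled proportion and SE1 the separate proportions.

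**Worked case, b = 30%, 58 per arm, no T0.**

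- Placebo: 0.30 + 0.70 × 0.20 = 0.440
- Ketamine: 0.30 + 0.70 × 0.45 = 0.615
- Difference: 0.175 = 0.70 × 0.25
- SE0 = √(2 × 0.5275 × 0.4725 / 58) = 0.0927
- SE1 = √((0.44 × 0.56 + 0.615 × 0.385) / 58) = 0.0913
- Power = Φ((0.175 - 1.96 × 0.0927) / 0.0913) = 47%

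With T0, new onset over all patients is 0.140 versus 0.315. The difference is still 17.5 points, but the variance is smaller, and power is 62%. Among the 0.70 × 58 = 40.6 per arm free of the symptom at T0, the full 25 points return and power is 68%.

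**Range, 58 per arm.**

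| b | Observed difference without T0 (points) | Power, no T0 | Power, T0, all patients | Power, T0, symptom-free |
|---|---|---|---|---|
| 0% | 25.0 | 83% | 83% | 83% |
| 20% | 20.0 | 58.1% | 69.5% | 73.7% |
| 30% | 17.5 | 47.1% | 61.6% | 67.8% |
| 50% | 12.5 | 29.4% | 44.5% | 53.0% |

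With 80 per arm and b = 30%, the three powers are 60%, 76% and 82%. With other assumed rates (10% versus 30%), b = 30% and 80 per arm, they are 43%, 73% and 76%.

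**No true excess.** If qK = qP, the expected difference is (1-b) × 0 = 0 at every b.

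The benefit of a T0 reading is the gap between the no-T0 and T0 columns, not the distance back to 83%. The model gives no credit for counting worsening, or a different new item in a patient who already had one.

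**The case against.** A reader might infer that every pre-existing symptom will be counted as a drug effect. The documents do not support that. Onset times are recorded, natural consequences of the admission reason are kept out of the eCRF, and relatedness is judged yes or no. A patient can also be asked at 10 min whether the nausea began before the injection. These safeguards stand, but only in part. The protocol does not say that the exclusion or the relatedness judgement applies to the prompted list. The SAP does not say that its comparison uses onset or relatedness. Without a T0 record, each rests on recall or judgement.

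A reader might also infer that a ketamine excess will be hidden, or a spurious one created. Randomisation balances pre-existing symptoms on average, so the effect is dilution: no false excess and no inflated type I error. Double vision, hallucinations and other items rare at baseline lose little.

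Restlessness from pain scored as agitation is tempting too, but it appears only as RASS +1, and the SAP names no agitation comparison. Sedation at T0 should be limited, because patients give written consent and those clearly influenced by drugs or alcohol are excluded. The SAP's sedation category is also named on the Ramsay scale, not RASS. The RASS part of the point is therefore the weaker one.

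The rates are assumptions, and a 25-point excess is more than sections 1.2.3 and 1.2.4 lead one to expect. Finally, section 6.2.1 says "Below is provided a brief overview of the included variables, but details are reserved for the data dictionary", and the SAP refers to a more detailed plan in the Trial Master File. Neither was available, so a coding rule may exist there. The published schedule would still have no T0 mark.

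**Conclusion.** The point holds as a dilution problem in a secondary safety comparison. Two gaps act together: no T0 reading of the patient-reported items or RASS, and no new-or-worsened rule in the SAP. Any true excess in a symptom common before dosing is reduced by the factor (1-b) in an any-report comparison, and the power to detect it falls.

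Under the assumed 20% versus 45% and 58 per arm, for b from 20% to 50%, power runs from 58% down to 29% without T0. With T0 it runs from about 70-74% down to 45-53%. A T0 reading therefore recovers part of the loss, about 15 to 21 points at b = 30%. These figures illustrate the mechanism and do not forecast this trial. The direction is certain wherever b is above zero and the safeguards are not applied in the analysis; the size is unknown. The primary outcome is untouched. The change should be made, because it is cheap and the dilution favours the hypothesis of similar side effects.

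**What to change.** Add a T0 mark, before study medication, for the patient-reported items and for RASS in the section 2.5.1 schedule and in section 6.2.2. In the SAP, define the analysed side effect as an item that is new or worsened since T0, name the denominator, and read RASS against its T0 value. The cost is about a minute of verbal questions, when the PI is already at the bedside for NRS and study medication, plus eCRF fields. The downside is that a symptom already present needs a simple worse-or-same note.

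The SAP speaks of all included patients as 116, so enrolment may be over and T0 data may no longer be obtainable. In that case, state before unblinding that recorded onset times define new symptoms. Report the any-report comparison beside that analysis, labelled as symptom prevalence rather than side effects of treatment, and name the missing T0 reading as a limitation. This costs a short SAP addendum and one extra table. Onset recalled at 10 min is weaker evidence than a T0 answer, and the report should say so.
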